## 5.1.1.2 Potential Systemic Risks

Systemic side effects of FHTR2163 are not anticipated based on data from the nonclinical studies and the Phase I clinical study. Observed systemic levels of FHTR2163 following multiple ITV administrations of 20 mg in the Phase I study (GR39821; see Section 1.3.2) were less than 0.2  $\mu$ g/mL on average at maximum concentration and are estimated to be at least 7,500-fold lower than vitreal FHTR2163 concentrations. On the basis of the binding affinity of FHTR2163, baseline systemic HtrA1 levels, and the systemic concentrations of FHTR2163 following ITV administration of 20 mg, complete inhibition of systemic HtrA1 is not expected.

Furthermore, there is a rare human disease, characterized by complete loss of HtrA1 activity due to a loss of function mutation in the HTRA1 gene, called cerebral autosomal recessive arteriopathy with subcortical infarcts and leukoencephalopathy (CARASIL). The main clinical manifestations of CARASIL are ischemic stroke or stepwise deteriorations in brain functions, progressive dementia, premature baldness, and attack of severe low back pain or spondylosis deformans/disc herniations. Even with complete

loss of HtrA1 activity from birth, the onset of clinical signs and symptoms do not manifest until 20 to 45 years of age (Hara et al. 2009; Fukutake 2011).

On the basis of the extended time course for the onset of CARASIL as well as the expectation that systemic exposures of FHTR2163 after ITV administration will not result in complete inhibition of systemic HtrA1, it is highly unlikely that patients will exhibit signs and/or symptoms of CARASIL after ITV administration of FHTR2163.

As part of the safety plan, masked aggregate adverse event reports will be reviewed periodically to assess for any potential systemic safety effect with specific focus on adverse events that may be related CARASIL signs and symptoms, and an IMC will review unmasked data on a regular basis to assess for any imbalances in rates of adverse events across different treatment arms (see Section 3.1.2 and the IMC Agreement for further details).

# 5.1.2 Risks Associated with Intravitreal Route of Administration

Potential ocular safety issues currently thought to be associated with the ITV route of administration include decreased BCVA, conjunctival hemorrhage, ocular inflammation (see Appendix 6 for anterior chamber and vitreous inflammation grading scales), intraocular infection (endophthalmitis), transient and/or sustained elevation of IOP, transient vision loss, cataract development or progression, retinal or vitreous hemorrhage, and retinal break or detachment. See Section 5.1.5 for details on management and Table 1 for instructions concerning dose-interruption and treatment discontinuation criteria.

An IMC will review unmasked data on a regular basis to assess for any imbalances in rates of adverse events due to ITV injections across different treatment arms (see Section 3.1.2 and the IMC Agreement for further details).

# 5.1.3 Risks Associated with Aqueous Humor Sampling through Anterior Chamber Paracentesis

Sampling of aqueous humor through anterior chamber paracentesis is a valuable procedure in providing samples for assessment of ocular PK and PD parameters of FHTR2163. Potential ocular safety issues may include cataract development or progression, anterior chamber hemorrhage, decreased IOP and/or hypotony, and decreased BCVA. There have also been rare reports of serious complications, including endophthalmitis and corneal abscess.

The procedure will be performed by experienced ophthalmologists familiar with aqueous humor sampling through anterior chamber paracentesis (see Appendix 14 for anterior chamber paracentesis and aqueous humor sampling procedures), and patients will be monitored closely for occurrence of any potential adverse event associated with the procedure.

# 5.1.4 Management of Patients Who Experience Adverse Events Associated with Intravitreal Injection

Following the study drug injection, patients will remain at the clinic for at least 30 minutes. IOP will be measured in both eyes before injection and in the study eye 30-50 minutes after injection. If there are no safety concerns, the patient will be discharged from the clinic. If the IOP is increased by  $\geq 10$  mmHg from the pre-injection measurement or is of concern to the investigator, the IOP will be measured again at 60-80 minutes post-injection. If the IOP value remains a concern to the investigator, the patient will remain in the clinic and will be treated as necessary in accordance with investigator's clinical judgment prior to the patient's discharge. For guidance on adverse event reporting, see Section 5.3.5.2. During each drug administration visit, finger counting will be tested within 15 minutes after study drug injection by the investigator; hand motion and light perception will be tested when necessary.

[figure not shown]
In addition, patients will be instructed by study site personnel about warning signs and symptoms, including decrease in vision, eye pain, unusual redness, or any other new ocular symptoms in the study eye. If warranted, patients will be asked to return to the clinic as soon as possible for an unscheduled safety assessment visit (see Appendix 1 and Appendix 2) and will be instructed to contact the investigator at any time should they have any health-related concerns. Please see Table 1 and Section 5.1.5 for instructions concerning dose-interruption and treatment discontinuation criteria, and management of IOI.

[figure not shown]
# 5.1.5 Dose-Interruption and/or Treatment Discontinuation Criteria

Study-treatment interruption and patient discontinuation from the study treatment for adverse events will be determined using the criteria listed in Table 1. If treatment is interrupted, treatment will not be resumed earlier than the next scheduled study visit. The reason for study treatment interruption or discontinuation should be recorded on the appropriate eCRF and, if applicable, on the Adverse Event eCRF (see Section 5.2.1 for definition of an adverse event). Adverse events should be reported to the Sponsor in accordance with instructions provided in Sections 5.2–5.6.

In addition, for any patient who develops any of the exclusion criteria (Section 4.1.2) after study onset, dosing may be interrupted or the patient may be discontinued from study treatment after discussion with the Medial Monitor.

Additionally, patients who receive any of the prohibited therapies (Section 4.4.2) may have study treatment interrupted or discontinued and/or may be discontinued from the study.

# 5.2 SAFETY PARAMETERS AND DEFINITIONS

Safety assessments will consist of monitoring and recording adverse events, including serious adverse events and adverse events of special interest, performing

protocol-specified safety laboratory assessments, measuring protocol-specified vital signs, and conducting other protocol-specified tests that are deemed critical to the safety evaluation of the study.

Certain types of events require immediate reporting to the Sponsor, as outlined in Section 5.4.

## 5.2.1 Adverse Events

According to the ICH guideline for Good Clinical Practice, an adverse event is any untoward medical occurrence in a clinical investigation patient administered a pharmaceutical product, regardless of causal attribution. An adverse event can, therefore, be any of the following:

- Any unfavorable and unintended sign (including an abnormal laboratory finding), symptom, or disease temporally associated with the use of a medicinal product, whether or not considered related to the medicinal product
- Any new disease or exacerbation of an existing disease (a worsening in the character, frequency, or severity of a known condition), (see Sections 5.3.5.11 and Section 5.3.5.12 for more information)
- Recurrence of an intermittent medical condition (e.g., headache) not present at baseline
- Any deterioration in a laboratory value or other clinical test that is associated with symptoms or leads to a change in study treatment or concomitant treatment or discontinuation from study drug
- Adverse events that are related to a protocol-mandated intervention, including those that occur prior to assignment of study treatment

# 5.2.2 Serious Adverse Events (Immediately Reportable to the Sponsor)

A serious adverse event is any adverse event that meets any of the following criteria:

- Is fatal (i.e., the adverse event actually causes or leads to death)
- Is life threatening (i.e., the adverse event, in the view of the investigator, places the patient at immediate risk of death)

This does not include any adverse event that, had it occurred in a more severe form or was allowed to continue, might have caused death.

- Requires or prolongs patient hospitalization (see Section 5.3.5.13)
- Results in persistent or significant disability/incapacity (i.e., the adverse event results in substantial disruption of the patient's ability to conduct normal life functions)
- Is a significant medical event in the investigator's judgment (e.g., may jeopardize the
  patient or may require medical/surgical intervention to prevent one of the outcomes
  listed above)

The terms "severe" and "serious" are not synonymous. Severity refers to the intensity of an adverse event (e.g., rated as mild, moderate, or severe, or according to National Cancer Institute Common Terminology Criteria for Adverse Events; see Section 5.3.3); the event itself may be of relatively minor medical significance (such as severe headache without any further findings).

Severity and seriousness need to be independently assessed for each adverse event recorded on the eCRF.

Serious adverse events are required to be reported by the investigator to the Sponsor immediately (i.e., no more than 24 hours after learning of the event; see Section 5.4.2 for reporting instructions).

# 5.2.3 Adverse Events of Special Interest (Immediately Reportable to the Sponsor)

Adverse events of special interest are required to be reported by the investigator to the Sponsor immediately (i.e., no more than 24 hours after learning of the event; see Section 5.4.2 for reporting instructions). Adverse events of special interest for this study are as follows:

- Cases of potential drug-induced liver injury that include an elevated ALT or AST in combination with either an elevated bilirubin or clinical jaundice, as defined by Hy's Law (see Section 5.3.5.9)
- Suspected transmission of an infectious agent by the study drug, as defined below
  Any organism, virus, or infectious particle (e.g., prion protein transmitting
  transmissible spongiform encephalopathy), pathogenic or non-pathogenic, is
  considered an infectious agent. A transmission of an infectious agent may be
  suspected from clinical symptoms or laboratory findings that indicate an
  infection in a patient exposed to a medicinal product. This term applies only
  when a contamination of the study drug is suspected.
- Adverse events resulting from medication error (see Section 5.3.5.14)

  Examples of medication errors include, but are not limited to over

Examples of medication errors include, but are not limited to, overdose, incorrect dose, incorrect route, incorrect drug, incorrect administration, or incorrect kit.

Sight-threatening adverse events

All sight-threatening adverse events listed below should be reported as serious adverse events, with the underlying cause (if known) of the event listed as the primary event term.

An adverse event is considered to be sight threatening and should be reported expeditiously if it meets one or more of the following criteria:

- It causes a decrease of ≥30 letters in VA score, compared with the most recent prior VA assessment, that lasts more than 1 hour and is attributable to study drug.
- It requires surgical intervention (i.e., conventional surgery, vitreous tap, or biopsy with ITV injection of an anti-infective compound; or laser or retinal cryopexy with gas) to prevent permanent loss of sight.
- It is associated with severe (Grade 4+) IOI and/or IOI-associated retinal vasculitis as defined in Section 5.3.5.1 (see Section 5.1.1.1 for further details on potential ocular risks, Table 1 for dose-interruption and treatment-discontinuation criteria, and Appendix 6 for IOI grading scales).

An additional ADA and PK sample should be collected as close as possible to the time of diagnosis (see Section 5.1.5 and Appendix 1 and Appendix 2).

 In the opinion of the investigator, it may require medical intervention to prevent permanent loss of sight.

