### Safety Objective

The safety objective for this study is to evaluate the local and systemic safety and tolerability of ITV injections of 20 mg FHTR2163 administered Q4W or Q8W relative to sham control on the basis of the following endpoints:

- Frequency, severity, and timing of ocular and systemic adverse events, serious adverse events, adverse events leading to study discontinuation, and adverse events of special interest
- Frequency, severity, and timing of notable findings in ocular examinations and ocular imaging, including those requiring intervention or start of anti-vascular endothelial growth factor (anti-VEGF) therapy
- Incidence of neovascular AMD diagnosed during the conduct of the study

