# 5.2.4 Selected Adverse Events

Additional data will be collected for the following selected adverse events:

- Loss of VA ≥30 letters, compared with the last assessment of VA prior to the most recent assessment, lasting more than 1 hour due to study drug treatment
- CNV conversion requiring treatment for either the study eye or non-study eye
- Any clinically significant ocular imaging finding

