Appendix 1: Schedule of Activities: Q4W Arms

			D	ay									We	eek \	/isit										
	PreBL Scrn a	BL Scrn b	1	8	4	8	12	16	20	24	28	32	36	40	44	48	52	56	60	64	68	72	76°		
Assessment Windows (Days)	–120 to –31	-30 to -1	_	±2	±5	±5	±5	±5	±5	±5	±5	±5	±5	±5	±5	±5	±5	±5	±5	±5	±5	±5	±5	UV	Early Term d
Whole blood sample for biomarkers (clinical genotyping)			х																						
Serum ADA sample			X		х		х			х						х						х		χ I, q	X
Serum PK sample for drug concentration			x	х	х		х			х						х						х	x	X I, q	х
BCVA testing (starting at 4 m) r	х	х	x	х	х	х	х	х	х	х	х	X	х	х	х	х	х	х	х	х	х	х	x	х	х
LL BCVA testing (starting at 4 m) r		х								x						х						х		х¹	
IOP measurement r	х	х	X	х	х	Х	х	х	х	Х	х	Х	Х	х	х	х	х	х	х	X	х	х	Х	Х	Х
Slit lamp examination s	х	Х	X	х	х	х	х	х	х	х	х	X	х	х	х	х	х	Х	х	X	х	х	Х	Х	X
Aqueous humor sample t			X		х					х						х							Х	χI	
Dilated binocular indirect ophthalmoscopy	х	х	x	х	х	х	х	х	х	х	х	х	х	х	х	х	х	х	х	x	х	х	x	х¹	х
FAF u	х	X k								х						х						х		χI	X
Keratometry u, v	х	Х																							
SD-OCT u	х	X		х		х		х		X		X		х		х		х		x		х		X I, q	X
OCT-A u, w		Х								х						х						х		χI	X
NI u	х	х								х						х						х		χI	X
Color fundus photography u		X																				х		χ I, q	X

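### The ≥30-letter vision-loss criterion is measured from the previous test, 4 weeks back on Q4W and 8 weeks back on Q8W, so its counts are not comparable between schedules, in a direction that depends on the pattern of loss

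*Combined protocol and SAP*

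**What the plan says.** Section 5.2.3 lists sight-threatening events among the AESIs and adds that "All sight-threatening adverse events listed below should be reported as serious adverse events". An event "should be reported expeditiously if it meets one or more of the following criteria". There are four criteria. The first is the letter-loss criterion: "It causes a decrease of ≥30 letters in VA score, compared with the most recent prior VA assessment, that lasts more than 1 hour". It carries a further condition: the loss is one "that lasts more than 1 hour and is attributable to study drug". The other three cover surgical intervention, Grade 4+ intraocular inflammation or associated retinal vasculitis, and a judgment criterion: "In the opinion of the investigator, it may require medical intervention to prevent permanent loss of sight".

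Section 5.2.4 collects additional data on a similar event but words the reference differently: "Loss of VA ≥30 letters, compared with the last assessment of VA prior to the most recent assessment". Neither section refers to baseline.

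The schedules have a row "BCVA testing (starting at 4 m") in each appendix. In Appendix 1 (Q4W) it is marked at Day 1, Day 8 and every 4 weeks from Week 4 to Week 76. In Appendix 2 (Q8W) it is marked at Day 1, Day 8, every 8 weeks from Week 8 to Week 72, and Week 76. Both also mark it at unscheduled visits.

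The safety objective (Synopsis and Section 2.2) counts, relative to sham control, adverse events, SAEs, "adverse events leading to study discontinuation, and adverse events of special interest". Section 6.5 plans descriptive summaries that include BCVA, and names no category of loss from baseline. Section 6.4.2 analyses mean BCVA change to Week 72.

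**The concern.** A criterion defined by loss since the previous test depends on how far apart the tests are. The regular spacing differs by a factor of two between the Q4W and Q8W schedules, so the same course of vision loss can be counted in one arm and missed in another with no difference in drug effect.

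The count feeds the AESI and SAE frequencies, which are safety endpoints, and Sections 5.1.1.1, 5.1.1.2 and 5.1.2 have the Internal Monitoring Committee review unmasked data for imbalances across arms. Section 5.1.1.1 already reports serious vitritis and uveitis in this study. An apparent difference in severe vision loss between the two active regimens, or the lack of one, could therefore reflect the visit calendar.

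**Working it through.** **Inputs from the documents.** Threshold: 30 letters (5.2.3). Q4W tests after Day 1: 20, with gaps of 1, 3, then 4 weeks (Appendix 1). Q8W tests after Day 1: 11, with gaps of 1, 7, eight of 8, then 4 weeks (Appendix 2). The plan states no expected rate on this criterion, so there is no figure to reproduce.

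**Assumed, because the documents are silent.** Size, speed and permanence of the loss; straight-line decline; onset spread evenly over time; test-retest SD 4 letters per test (range 2 to 6). Scheduled visits only, none missed. The attribution condition is set aside, so these are probabilities that the letter criterion alone is met.

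**1. Slope needed at regular visits.** 30/4 = 7.5 letters per week on Q4W; 30/8 = 3.75 on Q8W. Without noise, a steady decline slower than this never meets the criterion at those visits.

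**2. Permanent linear loss, no noise.** If L letters are lost over T weeks, 30 letters take w = 30T/L weeks. The event is counted only if one gap contains at least w weeks of the decline. For 40 letters over 8 weeks, w = 30 × 8/40 = 6. A 4-week gap cannot hold 6 weeks, so the probability is 0. With 8-week gaps and onset s weeks after a test, the two overlaps are 8 − s and s. One of them reaches 6 if s ≤ 2 or s ≥ 6, so the probability is (2 + 2)/8 = 0.50. Simulation over the full schedules, including the irregular gaps, gives:

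| Letters lost | Over (weeks) | Q4W | Q8W |
|---|---|---|---|
| 40 | 0 (abrupt) | 1.00 | 1.00 |
| 40 | 2 | 0.75 | 0.87 |
| 40 | 4 | 0.50 | 0.75 |
| 40 | 6 | 0.00 | 0.62 |
| 40 | 8 | 0.00 | 0.50 |
| 40 | 12 | 0.00 | 0.00 |
| 45 | 12 | 0.00 | 0.50 |
| 60 | 8 | 1.00 | 1.00 |
| 60 | 12 | 0.00 | 1.00 |
| 60 | 16 | 0.00 | 1.00 |
| 35–45 | 24 | 0.00 | 0.00 |

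The 60-letter, 16-week case sits exactly on the boundary (60/16 = 3.75).

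**3. Adding test noise.** With SD 4 per test, 40 letters over 8 weeks is counted in about 5% v 51%. With SD 2 it is 0% v 50%, and with SD 6 it is 17% v 52%. The boundary case of 60 letters over 16 weeks becomes about 1% v 61% at SD 4.

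**4. Abrupt loss of more than 30 letters that recovers after D weeks.** It is seen only if a test falls in the window, with probability min(1, D/gap):

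| D (weeks) | Q4W | Q8W |
|---|---|---|
| 1 | 0.25 | 0.125 |
| 2 | 0.50 | 0.25 |
| 4 | 1.00 | 0.50 |
| 8 | 1.00 | 1.00 |

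Here Q4W counts more.

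**5. Noise only.** Q4W has 20 consecutive comparisons and Q8W has 11. The chance of at least one false 30-letter drop is 2.7% v 1.5% if the SD of the change between tests is 10 letters, and 11.7% v 6.7% if it is 12. At SD 4 per test the SD of change is 4√2 = 5.7 and false drops are negligible on both schedules.

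**6. Baseline reference at common visits.** Weeks 8, 16 … 72 give every arm the same 72/8 = 9 looks, so losses, recoveries and noise are sampled alike. Without noise, a permanent loss that reaches 30 letters by Week 72 is always counted. With SD 4, 40 letters over 8 weeks (onset Weeks 4 to 60) is counted in 99.6%.

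**The case against.** Several objections carry weight.

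- **Direction.** A reader might infer that Q4W always under-counts. Steps 2, 4 and 5 contradict that: abrupt permanent loss is counted equally, as is 60 letters over 8 weeks, and short-lived losses and noise are counted more on Q4W. The criterion needs only more than 1 hour's duration, so brief losses are within its scope.
- **Sham.** A reader might infer a bias in favour of Q4W and against Q8W relative to a sham group pooled over both schedules. The documents do not support this. The criterion requires attribution to study drug, which sham patients do not receive, so read strictly it should yield almost nothing on sham at either spacing. Pooling of sham is stated for sample size and efficacy (6.1, 6.4). Section 6.5 groups safety by treatment received and does not mention pooling, and each schedule has its own sham arm.
- **Gradual loss.** A reader might infer that slow severe loss is never reported. That is true only of this criterion. The judgment criterion has no letter threshold or reference visit. Section 5.2.2 makes persistent or significant disability serious. Section 5.3.5.12 applies the sight-threatening rules to unexpected worsening of atrophy, and leaves expected progression out by design.
- **Size.** The percentages rest on assumed losses at scheduled visits. Calls 14 (±5) days after each treatment (4.5.7), prompt evaluation and unscheduled BCVA tests would narrow the gap by an amount that cannot be computed here.
- **Purpose and coverage.** The criterion is an expedited-reporting trigger. The Data Analysis Plan and Table 1 of Section 5.1.5 are not in the text available for this review and may contain a relevant rule or table.

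None of this makes the criterion schedule-neutral. The judgment criterion is applied by investigators who are not masked, whereas the BCVA examiner is masked (4.2.2). Mean change can hide a few severe losses.

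**Conclusion.** Counts on the ≥30-letter criterion are not comparable between the Q4W and Q8W schedules. Q4W tends to count fewer permanent losses that develop over about 2 to 16 weeks (about 5% v 51% for 40 letters over 8 weeks at SD 4), the same number of abrupt permanent losses, and more losses that recover within 8 weeks or arise from noise. The net direction is unknown because the documents do not say which pattern to expect. Slow loss does not meet this criterion on either schedule, though other criteria and rules may capture it.

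The comparison affected is chiefly Q4W v Q8W. No bias against sham can be put into figures. The criterion is serviceable as a reporting trigger; the weakness lies in using its counts to compare arms. This is a modest point with an inexpensive remedy.

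**What to change.** 1. Leave the expedited-reporting trigger in 5.2.3 as it is.
2. Reconcile the reference assessment in 5.2.3 and 5.2.4. The wording in 5.2.4 can be read as the same preceding test or as one test further back.
3. Add to Section 6.5 (and the Data Analysis Plan, unless already there), by arm, the number of patients whose study eye lost ≥30 letters, and ≥15 letters, from baseline at the BCVA visits common to all arms (Weeks 8, 16 … 72), regardless of attribution. State which pre-treatment test is the baseline, since BCVA is done at both screening and Day 1.
4. Base the between-arm comparison of severe vision loss on that count, not on the AESI criterion.

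The cost is a few lines of text and one table from BCVA data already collected. The downside is that short-lived losses between common visits drop out of this count: by step 4, a 4-week loss is seen with probability 0.50 in every arm, against 1.00 on the full Q4W schedule. Those that are reported remain in the AE and AESI listings.
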